### 3.3 Statistical Principles

#### 3.3.1 General Principles of Analysis

The statistical analyses will be reported using summary tables, figures, and data listings. All analyses and tabulations will be performed using SAS® Version 9.3 or higher. All tables, listings, and figures will be validated and reviewed before being finalized.

In summary tables of continuous variables, the minimum and maximum will be presented to the same number of decimal places as the original data. The mean, median, standard deviation (SD), standard error (SE), and 95% confidence interval (CI) will be presented to one more decimal place than the original data.

In summary tables of categorical variables, count and percentage will be provided. In general, percentage values are to be presented to whole number if sample size  $\leq 100$ ; to one decimal place if sample size is between 100 and 1000; and to two decimal places if sample size is greater than 1000. Any test of comparison performed will be 2-sided at 5% level of significance unless otherwise specified.

#### 3.3.2 Baseline Value

Baseline value will be defined as the most recent non-missing measurements collected prior to the first dose of study treatment. If there is more than one value on or before the date of the first dose of study treatment, the values closest to and prior to (including on) the date of the first dose will be used as the baseline value. Change from baseline will be defined as post-baseline value minus baseline value.

#### 3.3.3 Handling of Missing Data

Missing data will not be imputed. All data will be presented as collected.

#### 3.3.4 Pooling of Data

Data from all sites will be combined for the purpose of data summary and analysis. The number of patients enrolled by study site will be reported. For the primary analysis, data from all exon 20 mutations regardless of the position and designation will also be combined.

#### 3.3.5 Analysis Population

- The **As-Treated Population** will be the primary analysis population and include all patients who receive at least one dose of study medication.
- The **Evaluable Population** consists of all patients who are enrolled, have at least one dose of poziotinib treatment, and is evaluable for tumor response based on RECIST, Version 1.1, by central imaging review. The efficacy data will also be analyzed using the **Evaluable Population**.

The **Evaluable Population** will exclude patients whose best overall response is NE as well as patients who do not have target lesion at baseline, all based on the central imaging review by IRC at Bioclinica.

- The **Safety Analysis Population** includes all patients who signed informed consent, enrolled, and received at least one dose of study treatment. All demographics, baseline characteristics, and safety data will be analyzed using the **Safety Analysis Population**.

### 3.4 Futility Analysis

The study includes a futility analysis to be conducted in each patient cohort when the response rate for the first 20 patients in that cohort is available. A patient cohort will be stopped for futility if the ORR is <10%. No adjustment to multiplicity will be made for the futility analysis.

### 3.5 Final Analysis

The final analysis will be performed separately for each cohort as if they are independent studies. Although the study is ongoing, the database for a patient cohort will be closed and locked for the final full study analysis separately when all patients in that cohort complete 24-month follow-up or discontinue from the study.

Primary endpoint only and full analysis will be conducted in the timeframe described below. For primary endpoint only analysis, data cutoff, data cleaning and data snapshot will be done before proceeding to analysis.

#### Primary Endpoint Analysis:

The primary endpoint is the ORR and is evaluated using the response evaluation (RECIST 1.1) data obtained from the IRC at Bioclinica. The timing of the primary endpoint analysis will be determined by taking into consideration the length of follow up, best overall response and possibility to confirm the responses in the primary analysis population and not necessarily at the completion of 24-month follow-up or discontinuation in all patients.

Data will be incomplete to have a full analysis of secondary endpoints such as DCR, DOR, PFS and QoL at the time of the primary endpoint analysis and will be truncated.

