### 2.1 Study Design and Treatment Plan

This is a Phase 2, open-label, single-arm, multicenter study to evaluate the efficacy and the safety/tolerability of poziotinib in various cohorts. Cohorts 1-4 of the study will enroll up to 174 NSCLC patients previously treated with any systemic therapy (87 patients with EGFR exon 20 insertion mutations and 87 patients with HER2 exon 20 insertion mutations) and up to 140 treatment-naïve NSCLC patients (70 patients with EGFR exon 20 insertion mutations and 70 patients with HER2 exon 20 insertion mutations).

The **Screening** period (**Day -30 to Day -1**) lasts up to approximately 30 days prior to **Cycle 1, Day 1**. Patients must meet all Inclusion/Exclusion Criteria to participate in the study. Eligible patients will provide written Informed Consent prior to undergoing any study procedures.

Each treatment cycle is 28 calendar days in duration. There will be four patient cohorts and eligible patients will be enrolled into each cohort in parallel based on EGFR or HER2 exon 20 mutant status and prior treatment status:

- **Cohort 1:** Previously treated patients with EGFR exon 20 insertion mutation positive metastatic NSCLC
- **Cohort 2:** Previously treated patients with HER2 exon 20 insertion mutation positive metastatic NSCLC
- **Cohort 3:** Treatment naïve patients with EGFR exon 20 insertion mutation positive metastatic NSCLC
- **Cohort 4:** Treatment naïve patients with HER2 exon 20 insertion mutation positive metastatic NSCLC

Toxicity will be assessed based on the grade of the adverse events (AEs) using CTCAE version 4.03.

Poziotinib will be taken orally, once daily (QD) with food and a glass of water at approximately the same time each morning. On **Day 1** of each 28-day cycle, the patient's absolute neutrophil count (ANC) must be  $\geq 1.5 \times 10^9/L$  and platelet count must be  $\geq 100 \times 10^9/L$  before administering poziotinib.

All patients will be treated until 24 months of treatment, disease progression, death, intolerable AEs, or other protocol-specified reason for patient withdrawal.

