## 3 STATISTICAL CONSIDERATIONS

This is a Phase 2, open-label, single-arm, multicenter study with seven patient cohorts and this SAP focuses on the first 4 cohorts. Each cohort is an independent study and will be analyzed separately at different time. For Cohorts 1-4 (ZENITH20-1, ZENITH20-2, ZENITH20-3, ZENITH20-4), all statistical summary tables, data listings, and figures will be produced separately with the corresponding clinical study reports. The statistical analyses and clinical study reports may be submitted to the Agency separately for each cohort.

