#### Full Cohort analysis:

Once all patients in a cohort complete the study or discontinue, the final database lock will be completed, and the final study analysis will be performed. At this time, all secondary endpoints and safety analysis will be performed.

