#### 5.1 Best Overall Response

For **As-Treated Population**, the best overall response is defined as the best response from the start of study treatment until PD or the last tumor assessment on study. A best overall response of

CR or PR requires confirmation at a subsequent visit that is  $\geq 4$  weeks after. One NE response before the confirmed evaluation is allowed. A best overall response of SD can only be made if the subject is on-treatment for  $\geq 6$  weeks. **Table 2** summarizes how best overall response is determined. Details are referred to Independent Review Charter.

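### The SAP sets the primary analysis date by considerations that include best overall response, with no objective trigger, minimum follow-up or requirement of complete enrolment

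*SAP*

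**What the plan says.** Section 3.5 (Final Analysis) separates a primary endpoint analysis from a full cohort analysis and announces a timeframe for both. Only the second receives a trigger: "Once all patients in a cohort complete the study or discontinue, the final database lock will be completed".

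For the primary analysis the SAP says: "The timing of the primary endpoint analysis will be determined by taking into consideration the length of follow up, best overall response". The same sentence then adds a third consideration and sets aside the 24-month milestone: "possibility to confirm the responses in the primary analysis population and not necessarily at the completion of 24-month follow-up or discontinuation in all patients". Section 3.5 also requires a data cut-off, cleaning and a snapshot beforehand, but does not say what prompts them.

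Related provisions:
- **Design.** Section 3: "This is a Phase 2, open-label, single-arm, multicenter study with seven patient cohorts and this SAP focuses on the first 4 cohorts".
- **Endpoint.** Section 3.5: "The primary endpoint is the ORR and is evaluated using the response evaluation (RECIST 1.1) data obtained from the IRC at Bioclinica". Section 5.2.1 derives ORR from confirmed best overall response and tests it with the 95% Clopper-Pearson interval.
- **Confirmation.** Section 5.1: "CR or PR requires confirmation at a subsequent visit", at least 4 weeks later.
- **Denominator.** Section 3.3.5, on the As-Treated Population: "will be the primary analysis population and include all patients who receive at least one dose of study medication".
- **Enrolment.** Section 2.1 gives a ceiling: "Cohorts 1-4 of the study will enroll up to 174 NSCLC patients", that is 87 in each of Cohorts 1 and 2. Cohorts 3 and 4 have a ceiling of 70 each.

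The SAP nowhere requires a cohort to be fully enrolled, or each treated patient to have reached a given scan, before the primary cut-off.

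**The concern.** The variable under test is named as an input to when it is tested. The error rate of a fixed-n interval test holds only if the cut-off, and hence n, does not depend on the responses. Because the study is open-label and single-arm, running response counts can be known to those choosing the date. Central reading by two readers and an adjudicator (Section 5) limits bias in the reads, but does not blind the choice of date.

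Two different harms are possible:
- If a cohort is still growing, a date chosen on the responses acts like repeated testing without error control.
- If the cohort is complete but immature, responses still awaiting confirmation count as failures, so ORR is understated and power is lost.

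Sections 3 and 3.2 treat each cohort as a standalone hypothesis test that may go to the Agency separately, so the trigger should be beyond dispute.

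**Working it through.** **Inputs from the SAP (Sections 3.2.1, 3.2.2 and 5.2.1).** Cohorts 1–2: n=87, p0=0.17, p1=0.30, stated power 85%. Cohorts 3–4: n=70, p0=0.20, p1=0.40, stated power 90%. Both use a two-sided 5% level. Success means that the Clopper-Pearson lower bound exceeds p0.

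**1. The plan's own figure.** Normal approximation: power = Φ{[(p1−p0) − 1.96·√(p0(1−p0)/n)] / √(p1(1−p1)/n)}.
- n=87: (0.13 − 1.96×0.0403)/0.0491 = 1.04, giving 85.1%. The stated 85% reproduces.
- n=70: (0.20 − 1.96×0.0478)/0.0586 = 1.82, giving 96.5%. This is above the stated 90%, so the size is more than adequate. The timing point does not depend on it.

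**2. Exact test at a single mature cut-off.** The smallest successful count is the least r whose lower bound exceeds p0.
- n=87: r=23 (lower bound 17.6%; 22 responders give 16.6%). P(X≥23 | 0.17) = 1.76%. P(X≥23 | 0.30) = 79.9%.
- n=70: r=22 (lower bound 20.9%; 21 responders give 19.6%). P(X≥22 | 0.20) = 1.59%. P(X≥22 | 0.40) = 94.5%.

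**3. Cut-off free to move while n is growing.** This is an exact recursion at the null for the chance that the lower bound exceeds p0 at any permitted n. The permitted n are assumptions, because the SAP gives none. Each patient's confirmed response is taken as known at once, which favours inflation. The futility look is left out; it can only stop a cohort, so this does not understate the error.

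| Permitted cut-offs (assumed) | One-sided error |
|---|---|
| n=87 only | 1.76% |
| 60, 87 | 2.85% |
| any n from 77 to 87 | 2.9% |
| 60, 70, 80, 87 | 3.75% |
| any n from 40 to 87 | 5.6% |
| n=70 only | 1.59% |
| 50, 60, 70 | 2.9% |
| any n from 60 to 70 | 3.1% |
| any n from 35 to 70 | 5.3% |

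The nominal one-sided level is 2.5%.

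**4. All patients treated, cut-off immature.** The denominator is fixed and the number of confirmed responders can only rise with time. Choosing the date therefore cannot produce more false successes than the mature analysis (1.76% or 1.59%). Let f be the share of eventual responses confirmed at the cut-off (an assumption); power is then P(X≥r | f·p1).

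| f | n=87 | n=70 |
|---|---|---|
| 1.0 | 79.9% | 94.5% |
| 0.9 | 58.8% (rate 27%) | 82.1% (rate 36%) |
| 0.8 | 33.6% (rate 24%) | 58.5% (rate 32%) |

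Each responder still unconfirmed costs 1/87 = 1.15 or 1/70 = 1.43 points of ORR.

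**5. How long confirmation takes.** After weeks 4 and 8, Section 2.3 schedules scans about every 8 weeks, within ±7 days (Amendments 1 and 2) or ±14 days (original protocol). A response first seen at week 8 is confirmed at the scan nominally at week 16, which may fall as early as about week 15 or 14. A response first seen at week 16 waits until about week 24.

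**The case against.** The strongest reply is that the three considerations together describe data maturity: whether best overall response can be determined and confirmed without waiting 24 months. On that reading nobody compares the running ORR with the threshold. This is a fair reading, and no provision of the SAP says that ORR is monitored against 17% or 20%. But the wording does not confine itself to that meaning.

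A reader might infer more than the text supports:
- **That the error rate is inflated as planned.** The SAP does not say so. Section 3.2 sets 87 and 70 as the sizes for the test, and Section 3.5 describes one primary analysis per cohort. What Section 3.5 relaxes is follow-up, not n. The only look at part of a cohort is futility at 20 patients (Section 3.4), which cannot declare success. The ceiling in Section 2.1 is not permission to test early. A cut-off before full enrolment is merely not excluded.
- **That confirmation is overlooked.** The same sentence names it. What is missing is a number: a consideration is not a minimum follow-up.
- **That truncated duration of response is a hidden defect.** Section 3.5 discloses the truncation and assigns secondary endpoints to the final lock, and Section 5.3.2 censors under Kaplan-Meier.
- **That ORR will be tested twice.** No second test is stated. A sentence saying so would only remove doubt.

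The protocol is not at hand and may fix a trigger. The SAP's sentence on timing does not refer to one.

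**Conclusion.** The point holds as a badly fixed rule. The primary analysis has no objective trigger, and the outcome itself is among the considerations that set its date.

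The size depends on which case applies. With a complete cohort, the more natural reading, false success stays at 1.76% or 1.59%. The cost then falls on the estimate and the power: at 90% confirmed, a loss of about 21 points of power in Cohorts 1–2 (79.9 − 58.8) and 12 in Cohorts 3–4 (94.5 − 82.1). With a cut-off before the cohort is full, one-sided error could reach about 2.9–5.6% or 2.9–5.3%. The upper ends require a free choice of date over roughly the second half of enrolment with responses known at once, so they are outer values and not an expectation. The look schedules and the confirmed fractions are both assumptions. The change should be made because these are standalone hypothesis tests and the repair is cheap.

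**What to change.** In Section 3.5:
- Delete best overall response from the timing criteria.
- State one primary test per cohort, after enrolment to that cohort closes, at a cut-off set without reference to observed responses.
- Set the cut-off when every treated patient either has discontinued or has a stated minimum follow-up that lets a first response be confirmed at the next scheduled scan. About 6 months from first dose (roughly 26 weeks) is one example: it covers the week-16 scan and the one after it at about week 24. A cut-off at week 16 would leave responses first seen at that scan unconfirmed.
- State that ORR in the full-cohort analysis is a descriptive update and does not re-test the hypothesis.

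The cost is SAP wording only, with no added patients or procedures. The sponsor gives up discretion over the date and may wait somewhat longer.

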#### Full Cohort analysis:

Once all patients in a cohort complete the study or discontinue, the final database lock will be completed, and the final study analysis will be performed. At this time, all secondary endpoints and safety analysis will be performed.

## 4 PATIENTS CHARACTERISTICS

Patient characteristics will be summarized for **Safety Analysis Population**. Corresponding patient data listings will be provided.

### 4.1 Patient Disposition

The number of patients in the **Safety Analysis Population** and the reasons for study discontinuation will be summarized with count and percentage. Reasons for patient discontinuation include

- Development of an AE that interferes with the patient's participation
- Initiation of non-protocol therapy
- Development of progressive disease (PD)
- Patient withdrawal of informed consent
- Delay of poziotinib administration for >28 days since last poziotinib administration
- Investigator decision

- Sponsor decision
- Lost to follow-up
- Pregnancy
- Death

Summary of enrollment by site will also be presented.

#### 4.2 Protocol Deviations

The following important protocol deviations will be summarized with count and percentage.

- Patients entered the study even though they did not satisfy the entry criteria.
- Patients developed withdrawal criteria during the study but were not withdrawn.
- All protocol deviations will be provided in patient data listings.

#### 4.3 Baseline Characteristics

Demographics including age, gender, ethnicity, race, and age groups (<65 and 65+; <75 and 75+) and other baseline disease characteristics will be summarized using descriptive statistics.

Baseline characteristics include BMI, smoking status, Eastern Cooperative Oncology Group (ECOG) performance status, ECG assessment, cardiac ejection fraction, lung cancer histopathology, staging, mutation type, and prior cancer therapy (EGFR/HER2 therapy, immunotherapy, Tyrosine-kinase inhibitor therapy, chemotherapy, surgery, and radiation therapy).

#### 4.4 Medical History

Medical history information will only be provided in patient data listings.

#### 4.5 Concomitant Medication

A concomitant medication is any medication that was taken either on the day of or after the administration of the first dose of poziotinib through the end of the study. This includes medications that started prior to the initiation of the first dose of poziotinib if the patient continues using it.

For all concomitant medications, count and percentage of patients will be presented by medication class and preferred name coded by the World Health Organization Drug (WHO Drug) dictionary. Patients with more than one medication of the same medication class or preferred name will be counted only once.

### 5 EFFICACY ANALYSIS

- All primary analysis of efficacy endpoints will be based on the **As-Treated Population** and the central imaging review by IRC at Bioclinica using 2 independent readers and 1 adjudicator paradigm.

#### 5.1 Best Overall Response

For **As-Treated Population**, the best overall response is defined as the best response from the start of study treatment until PD or the last tumor assessment on study. A best overall response of

CR or PR requires confirmation at a subsequent visit that is  $\geq 4$  weeks after. One NE response before the confirmed evaluation is allowed. A best overall response of SD can only be made if the subject is on-treatment for  $\geq 6$  weeks. **Table 2** summarizes how best overall response is determined. Details are referred to Independent Review Charter.

**Table 2 Determination of Confirmed Best Overall Response**

Initial Best Response (can start at any visit)	Response at Subsequent Visit	Best Overall Response
CR	CR 	CR
PR	PR  or unconfirmed CR 	PR
PR	SD (not followed by CR/PR)	SD
SD	SD or unconfirmed CR/PR	SD
CR or PR or SD	PD	SD  or PD 
CR or PR or SD	NE (no additional evaluable visit)	SD  or NE 
PD	Any	PD
NE	NE (no additional evaluable visit)	NE

 Confirmation scan needs to be  $\geq 4$  weeks from previous scan, 1 intervening NE is allowed.

 Confirmation scan needs to be  $\geq 4$  weeks from previous scan, 1 intervening NE/SD is allowed.

 If initial CR/PR/SD is  $\geq 6$  weeks on-treatment.

 If initial CR/PR/SD is  $< 6$  weeks on-treatment.

For the **Evaluable Population**, a modified best overall response, which requires confirmation scan to be  $\geq 3$  weeks from previous scan, will be applied because the study protocol allows 7 days window for tumor assessment ([Section 2.3](#)).

## 5.2 Primary Endpoint

### 5.2.1 Objective Response Rate (ORR)

The primary endpoint is ORR and is defined as the proportion of patients whose best overall response is confirmed to be CR or PR from the first dose of poziotinib until the last tumor assessment on study. The unconfirmed ORR, which does not require confirmation scans for CR/PR, will also be provided.

ORR and unconfirmed ORR will be estimated with count, percentage and 95% CI (Clopper-Pearson).

The test of hypothesis of the primary endpoint will be performed using the 95% CI. The prespecified primary endpoint criteria for each cohort is stated in [Section 3.2](#).

### 5.3 Secondary Endpoints

#### 5.3.1 Disease Control Rate (DCR)

DCR is defined as the proportion of patients whose best overall response is CR, PR, or SD from the first dose of poziotinib until the last tumor assessment on study.

DCR will be estimated with count, percentage and 95% CI (Clopper-Pearson).

#### 5.3.2 Duration of Response (DoR)

DoR will be evaluated only for patients who has CR or PR and is defined as the time (in months) from the date that response evaluation criteria are first met for CR or PR (whichever status is recorded first) until the first subsequent date that PD or death is documented. DoR of patients without documented PD or death will be censored at the time of last tumor assessment.

Distribution of DoR will be estimated using the Kaplan-Meier method and the median and quartiles of DoR time and the DoR rate at 3, 6, 9 and 12 months will be reported with corresponding 95% CI.

### 5.4 Exploratory Endpoints

#### 5.4.1 Progression-Free Survival (PFS)

PFS is defined as the time (in months) from the treatment start date to the first date of documented PD or death. PFS time for patients without documented PD or death will be censored at the date of last tumor assessment or the date of first treatment if there is no post-baseline tumor assessment.

Distribution of PFS time will be estimated using the Kaplan-Meier method. The median and quartiles of PFS time and the PFS rate at 3, 6, 9 and 12 months will be estimated with corresponding 95% CI.

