## 2.3 Tumor Assessments

This section provides general description of tumor assessments. All images acquired at baseline and follow-up will be sent to Bioclinica, Inc. for central radiographic review by an Independent Review Committee (IRC) for response evaluation based on RECIST criteria, Version 1.1 [2]. Details are found in Bioclinica Independent Review Charter for SPI-POZ-202, including a list of all pre-specified modifications from RECIST 1.1 criteria.

Patient eligibility for enrollment will be based on the scans performed before the patient signed the ICF and review by the Site Principal Investigator. After patient enrolled into the study, baseline tumor assessment is required. All baseline and follow-up tumor assessments must be performed using computed tomography (CT), positron emission tomography (PET)/CT, or magnetic resonance imaging (MRI). The baseline tumor assessment must be performed within 2 weeks prior to, or on **Cycle 1, Day 1**. In situation that images are incomplete at baseline evaluation (i.e. missing images from some body sites), the most recently available images of the missing body sites prior to baseline (ie. at Screening) may be sent to Bioclinica as part of baseline evaluation.

For patients with known brain metastases, a baseline brain MRI scan will also be performed to assess the status of brain metastases if present.

Tumor assessments will be performed at

- approximately 4 weeks (**Cycle 2, Day 1**) [ $\pm 7$  days], 8 weeks of treatment (**Cycle 3, Day 1** [ $\pm 14$  days]), and approximately every 8 weeks ( $\pm 14$  days) thereafter [Original Protocol]
- approximately 4 weeks (**Cycle 2, Day 1** [up to **Cycle 2, Day 7**]), 8 weeks (**Cycle 3, Day 1** [up to **Cycle 3, Day 7**, with at least 28 days from previous tumor assessment]), and approximately every 8 weeks ( $\pm 7$  days) thereafter [Amendment 1 & 2]

For each patient, subsequent tumor assessment must use the same radiographic technique performed at baseline, either CT, PET/CT, or MRI. Tumor assessments will be made according to RECIST criteria, Version 1.1 [2] using appropriate radiographic imaging or other techniques. Patient enrollment and clinical decisions will be based on local imaging review and the efficacy assessments for final analysis will be based on the central imaging review by IRC at Bioclinica.

Measurable and non-measurable lesions that will not be followed by radiographic methods should be documented appropriately.

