### 2.3.2 Follow-up Tumor Assessments

**Target lesions** are followed for tumor size, (i.e., longest diameter of TLs and short axis of LNs), and SOD are calculated for response evaluation using RECIST 1.1 criteria. At each tumor assessment, the tumor response of **target lesions** is determined as below.

- **Complete Response (CR):** Disappearance of all non-nodal target lesions and any pathological lymph nodes must have become normal (i.e., decrease in short axis to  $< 10$  mm).
- **Partial Response (PR):** At least a 30% decrease in SOD of target lesions, taking as reference the baseline SOD. Additionally, progression of target lesions must not be present.
- **Progressive Disease (PD):** At least a 20% increase in the SOD of target lesions, taking as reference the nadir SOD (or the baseline, if the baseline is the nadir value). In addition to the relative increase of 20% in SOD, the SOD must also demonstrate an absolute increase of  $\geq 5$  mm.
- **Stable Disease (SD):** Neither sufficient shrinkage of target lesions to qualify for PR, nor sufficient increase to qualify for PD.
- **Not Evaluable (NE):** If  $\geq$  one (1) target lesion is classified as NE for a particular time point, the SOD and percent change cannot be accurately determined and the Target Response will be NE for that time point. The only exception is if the SOD of the evaluable target lesions shows a  $\geq 20\%$  increase from the nadir SOD and an absolute increase of  $\geq 5$  mm. In this case, the Target Response will be PD.
- **Not Applicable (NA):** No target lesions were identified at baseline. Subjects with no target lesions will be evaluated based on the assessment of non-target lesions or the presence of new lesions.

**Non-target lesions** are assessed qualitatively with present, absent or unequivocal progression and tumor response is determined as below.

- **Complete Response (CR):** The nontarget lesion has fully resolved. The lymph node must be nonpathological in size ( $< 10$  mm in the short axis).
- **Non-CR/Non-PD:** Persistence of the non-target lesion.
- **Progressive Disease (PD):** The non-target site of disease has shown unequivocal progression.
- **Not Evaluable (NE):** Any non-target lesion which was present at baseline, but which subsequently became unevaluable.
- **Not Applicable (NA):** No non-target lesions identified at baseline.

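### The censoring rules for DoR and PFS do not require the last tumor assessment to be evaluable, so a final Not Evaluable scan can extend event-free time

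*SAP*

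**What the plan says.** Section 5.3.2 (DoR, secondary): "DoR of patients without documented PD or death will be censored at the time of last tumor assessment".

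Section 5.4.1 (PFS, exploratory): "PFS time for patients without documented PD or death will be censored at the date of last tumor assessment". With its fallback, the rule reads in full that such time is "censored at the date of last tumor assessment or the date of first treatment if there is no post-baseline tumor assessment". The fallback to first treatment therefore applies only when no scan was done after baseline.

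Section 2.3.2 makes NE a possible result of a scan that was performed. If one or more target lesions cannot be evaluated, "the SOD and percent change cannot be accurately determined and the Target Response will be NE for that time point". There is one exception: PD is still called if the evaluable target lesions alone meet the PD criteria. Table 1 carries NE through as a time point response, and only where there is no new lesion and no non-target PD.

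Table 2 foresees a series of scans that ends in NE. It has rows in which CR, PR or SD, or an earlier NE, is followed by "NE (no additional evaluable visit"), so it treats an NE visit as something other than an evaluable visit.

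No other section adds the word evaluable to the two censoring rules. Section 3.3.3 says only that missing data are not imputed. The Independent Review Charter is cited for response evaluation (Section 2.3) and best overall response (Section 5.1), not for censoring.

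**The concern.** Censoring at a date states that the patient was known to be event-free up to that date. At an NE scan the sum of diameters is, by the SAP's own account, not determinable, so the last date on which absence of progression was fully shown is the preceding evaluable scan. The SAP draws this distinction for best overall response and drops it for DoR and PFS.

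At stake are the Kaplan-Meier medians, quartiles and rates at 3, 6, 9 and 12 months for both endpoints. Each cohort is single-arm, so no control group shares the bias. DoR is also what gives a response rate its clinical meaning.

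**Working it through.** **1. The two rules applied to the same patient.**

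| Scan results | Table 2 best overall response | Censoring as written | Last evaluable scan |
|---|---|---|---|
| PR at weeks 8 and 16, NE at week 24, then off study | PR | Week 24 (DoR and PFS) | Week 16 |
| SD at week 4, NE at week 8, no further evaluable visit | NE (SD seen before 6 weeks) | Week 8 (PFS) | Week 4 |
| NE at week 4 only | NE | Week 4 (PFS) | None, so first treatment |

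In the second and third rows the SAP declines to credit disease control, yet credits progression-free time up to the NE scan.

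**2. Direction.** The Kaplan-Meier estimate is S(t) = ∏(1 − d/n) over event times. Moving a censoring date later can only leave n unchanged or increase it at the event times passed over, and d does not change. S(t) therefore rises or stays the same.

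**3. Size per patient.** Section 2.3 schedules scans at weeks 4 and 8 and then about every 8 weeks. One trailing NE scan moves the date by 4 × 7/30.4375 = 0.92 months or 8 × 7/30.4375 = 1.84 months. Two in the 8-week phase move it by 3.7 months.

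**4. Size for the curve.** The SAP gives no NE rate, no dropout rate and no figure that depends on this rule, so there is nothing to reproduce. Two illustrative models follow. Both use exponential progression and scans at weeks 4, 8, 16, 24 and so on. The 6-month rate is then fixed by the week-24 scan (5.52 months).

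*Model 1: NE falls on the progression scan.* A share q of patients have NE at the scan that would have shown progression, and they then leave. The assumed median is 2.7 months, the afatinib figure in Section 3.2. With h the probability of progression in an interval:

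- 4-week interval: 1 − h = 0.5^(0.92/2.7) = 0.790
- 8-week interval: 1 − h = 0.5^(1.84/2.7) = 0.624
- factor per scan as written: 1 − (1 − q)h
- factor per scan with last evaluable: (1 − h)/(1 − qh)

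| q | As written | Last evaluable | No NE scans |
|---|---|---|---|
| 10% | 0.8107² × 0.6612² = 0.287 | 0.8066² × 0.6479² = 0.273 | 0.5^(5.52/2.7) = 0.242 |
| 20% | 0.8317² × 0.6988² = 0.338 | 0.8243² × 0.6743² = 0.309 | 0.242 |

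A simulation of 400,000 patients gave 0.288 against 0.273 and 0.338 against 0.309, which agrees. With a median of 5.5 months it gave 0.539 against 0.532 and 0.580 against 0.567. At a median of 2.7 months the fix removes 1.4 of 4.5 points at q = 10% and 2.9 of 9.5 at q = 20%, about a third. The rest comes from the assumed dropout at progression. The Kaplan-Meier median is the same under both rules (3.68 months, and 7.36 in the 5.5-month case). The share of shifts that are 4 weeks long is 1 − 0.624, about 38%.

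*Model 2: NE unrelated to progression.* Each scan is NE with the assumed probability. Dropout after a scan is 10% if it was evaluable and 50% if it was NE. There were 200,000 simulated patients per row.

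| Assumed median (months) | NE per scan | 6-month PFS as written | Last evaluable | Difference (points) |
|---|---|---|---|---|
| 3 | 5% | 0.293 | 0.282 | 1.1 |
| 3 | 10% | 0.310 | 0.286 | 2.4 |
| 3 | 20% | 0.341 | 0.291 | 5.0 |
| 5.5 | 5% | 0.511 | 0.502 | 0.9 |
| 5.5 | 10% | 0.521 | 0.501 | 2.0 |
| 5.5 | 20% | 0.548 | 0.505 | 4.3 |
| 9 | 5% | 0.665 | 0.658 | 0.7 |
| 9 | 10% | 0.672 | 0.656 | 1.6 |
| 9 | 20% | 0.694 | 0.661 | 3.3 |

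With no NE scans the values would be 0.5^(5.52/3) = 0.279, 0.5^(5.52/5.5) = 0.499 and 0.5^(5.52/9) = 0.654. Here the fix removes most of the excess. The median was unchanged at 3 and 5.5 months and moved one scan step, from 11.0 to 9.2 months, at 9 months. The 20% rows are a heavy case: 27% to 38% of patients have their date moved.

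**The case against.** **The SAP is silent; it does not instruct the use of NE scans.** A reader might infer that it deliberately counts them. It does not say so. The defect is a missing qualifier, and a careful programmer might add it. That stands as a description, but the literal wording includes NE scans, and the choice should not be left to programming after the data are seen.

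**Tumor status at an NE scan is not simply unknown.** "The only exception is if the SOD of the evaluable target lesions shows a" large enough increase, in which case PD is called. A new lesion or non-target PD also makes the time point PD. An NE result therefore gives partial evidence against progression, and a reader who treats the whole interval as blank goes too far. Model 1 ignores this and is a worst case in that respect. The evidence can still be thin, because the NE row of Table 1 also accepts non-target lesions that are themselves NE.

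**NE scans may not cluster in deteriorating patients.** Such clustering is plausible, but nothing in the SAP supports it, so it remains an assumption. The upward direction does not depend on it: Model 2 shows the excess with NE unrelated to progression.

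**The Evaluable Population already deals with this.** Only in part. Section 3.3.5 removes patients whose best overall response is NE, but not those with a later NE scan after an evaluable result. Section 5.5.1 lists PFS but not DoR for that population, and Section 5 makes the As-Treated Population primary.

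**The endpoints are secondary or exploratory.** This stands. DoR is descriptive with no hypothesis test, and PFS is exploratory.

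**Conclusion.** The concern holds as a gap in two censoring rules that conflicts with the SAP's own treatment of NE. Its direction, upward or no change, follows from the text and the Kaplan-Meier formula. Its size does not. The figure of about 1 to 5 points on 6-month PFS rests on exponential progression and on assumed NE rates of 5% to 20% with assumed dropout.

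Three stronger readings are not supported. First, one might set a 1.8-month shift against the 2.4 to 2.7 month median PFS cited in Section 3.2. That compares one patient's censoring date with a population median, and the Kaplan-Meier median moved only at the assumed 9-month median. Second, one might expect the fix to make the estimates unbiased. If patients leave because they are progressing, most of the bias remains (about two thirds in Model 1). Third, one might carry the figures over to DoR. With 30% of 87, about 26 responders, each affected patient is about 4% of the DoR set, but that is a share of patients and not an effect. DoR was not modelled, and only the direction is known.

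The primary ORR is unaffected. The change is worth making before analysis because it is cheap and closes off a data-dependent choice.

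**What to change.** In Sections 5.3.2 and 5.4.1, censor patients without PD or death at the date of the last evaluable tumor assessment, defined as one with a time point response other than NE according to the review concerned (central or local). In Section 5.4.1, make first treatment the censoring date when there is no evaluable post-baseline assessment, instead of only when there is no post-baseline assessment at all. Apply the same rule to the local-review analyses in Section 5.5.4.

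The cost is one sentence in each section and one filter in the time-to-event datasets. The downside for the sponsor is that DoR and PFS may look slightly shorter.
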